7.10.2 Plasma Pharmacokinetic Parameters

The PK parameters of plasma TAK-071 will be determined from the concentration-time profiles for all evaluable subjects according to standard noncompartmental analysis methods by Takeda or its designee. Actual sampling times, rather than scheduled sampling times, will be used in all computations involving sampling times. The following PK parameters will be calculated:

Symbol/Term	Definition
Plasma	
AUC_{∞}	Area under the plasma concentration-time curve from time 0 to infinity, calculated using the observed value of the last quantifiable concentration using the equation: $AUC_{\infty} = AUC_{last} + C_{last}/\lambda_z$
AUC_{last}	Area under the concentration-time curve from time 0 to time of the last quantifiable concentration
AUC_{24}	Area under the concentration-time curve from time 0 to time 24 hours. $AUC_{24} = AUC_t$ at steady-state.
AUC_t	Area under the concentration-time curve from time 0 to time t
C_{max}	Maximum observed concentration.
CL/F	Apparent clearance after extravascular administration, calculated as $=Dose/AUC_{\infty}$.
CL/F _{ss}	Apparent clearance after extravascular administration at steady-state, calculated as $=Dose/AUC_{24}$.
λ_z	Terminal disposition rate constant, calculated as the negative of the slope of the log-linear regression of the natural logarithm concentration-time curve during the terminal phase.
$R_{ac(AUC)}$	Accumulation ratio based on AUC_{24} , calculated as $AUC_{24} (steady-state) / AUC_{\infty} (Day 1)$
$R_{ac(C_{max})}$	Accumulation ratio based on C_{max} , calculated as $C_{max} (steady-state) / C_{max} (Day 1)$
$t_{1/2z}$	Terminal disposition half-life, calculated as $\ln(2)/\lambda_z$.
t_{max}	Time to first occurrence of C_{max}
V_z/F	Apparent volume of distribution during the terminal disposition phase after extravascular administration, calculated using the observed value of the last quantifiable concentration using the equation: $(CL/F)/\lambda_z$.

For Cohort 17 the key PK parameters C_{max} , t_{max} , and AUC_{∞} will be determined.

In general, if AUC_{∞} cannot be accurately estimated in a sufficient number of subjects, AUC_{last} will be used for statistical analysis instead. Additional plasma PK parameters may be calculated if necessary, in accordance with the Clinical Pharmacology Analysis Plan (CPAP).

The plasma PK parameters of donepezil will be determined from the concentration-time profiles for all evaluable subjects according to standard noncompartmental analysis methods. Actual sampling times, rather than scheduled sampling times, will be used in all computations involving sampling times. The following PK parameters will be calculated: t_{max} , C_{max} , and AUC_{24} . Additional donepezil plasma PK parameters may be derived and/or reported as appropriate, in accordance with the CPAP.

Plasma PK parameters for TAK-071 will be listed and summarized separately for the TAK-071 SRD part (TAK-071 alone [Cohorts 1 to 6, 18, and 19]) or in presence of donepezil [Cohorts 20

to 22] for non-Japanese subjects), the MRD part (TAK-071 alone for non-Japanese subjects [Cohorts 7 to 9], TAK-071 alone for Japanese subjects [Cohorts 13 to 15], or TAK-071 in the presence of donepezil [Cohorts 10 to 12] for non-Japanese subjects), subjects with MCI or Mild AD (Cohort 16), and the relative BA/FE cohort (Cohort 17).

Plasma PK parameters for donepezil will be listed and summarized separately for the SRD part ([Cohorts 20 to 22] for non-Japanese subjects) and the MRD part ([Cohorts 10 to 12] for non-Japanese subjects). Plasma PK parameters for donepezil will also be listed and summarized for subjects with MCI or Mild AD (Cohort 16).

Descriptive statistics (including N, arithmetic mean, SD, %CV, median, minimum, maximum) will be used as appropriate. Geometric mean and %CV of the geometric mean will be reported for AUCs and C_{max} . All subjects with a valid PK parameter estimate will be included in the summaries and analyses for that parameter.

Dose proportionality for the SRD and MRD parts will be assessed (separately) using the empirical power law model [4]. This analysis will be carried out to assess the degree of dose proportionality based on the dose proportionality exponent (β) for the model for both C_{max} and AUC_{∞} on Day 1 (SRD) and for C_{max} and AUC_{24} at steady-state (Day 21 or 28 for MRD).

Dose linearity will be examined in the event that dose proportionality cannot be established by using a simple linear regression on the exposure parameter.

For the BA/FE cohort, PK parameters of TAK-071 will be summarized by regimen. A mixed effects analysis of variance (ANOVA) will be performed on natural logarithms of TAK-071 C_{max} and AUCs with sequence, period, and regimen as fixed effects and subject nested within sequence as a random effect. Within the framework of ANOVA, comparisons will be performed for tablet versus capsule and for fed versus fasting dosing condition to assess the relative bioavailability of TAK-071.

The ratios and the 90% CIs for the central values of each test regimen relative to the reference regimen will be provided. Wilcoxon signed-rank test will be used to compare t_{max} between the test and reference regimens.

In addition to the above, other PK analysis methodologies may be employed to further characterize the PK behavior of TAK-071 in healthy subjects, including conventional compartmental analyses and nonlinear mixed-effect modeling using TAK-071 pooled data across studies.

7.10.3 Urine Pharmacokinetic Concentrations

Collection of Urine Samples for Pharmacokinetic Analysis Cohorts 1 to 6, 18, and 19.

Analyte	Matrix	Dosing Day	Scheduled Time (hours)
TAK-071	Urine	1	Predose urine void within approximately 1 hour of dosing and (0 to 6), (6 to 12), (12 to 24), (24 to 48), (48 to 72), and (72 to 96) hours postdose

Collection of Urine Samples for Pharmacokinetic Analysis Cohorts 7 and 8.

Analyte	Matrix	Dosing Day	Scheduled Time (hours)
TAK-071	Urine	1	Predose urine void within approximately 1 hour of dosing and (0 to 6), (6 to 12), and (12 to 24) hours postdose
TAK-071	Urine	21	(0 to 6), (6 to 12), and (12 to 24) hours after the last dose

Note: Subjects should void urine prior to dosing on Day 21.

Collection of Urine Samples for Pharmacokinetic Analysis Cohorts 9 and 13 to 15.

Analyte	Matrix	Dosing Day	Scheduled Time (hours)
TAK-071	Urine	1	Predose urine void within approximately 1 hour of dosing and (0 to 6), (6 to 12), (12 to 24), (24 to 48), (48 to 72), and (72 to 96) hours postdose
TAK-071	Urine	28	(0 to 6), (6 to 12), and (12 to 24) hours postdose

Note: Subjects should void urine prior to dosing on Day 28.

Collection of Urine Samples for Pharmacokinetic Analysis Cohort 16.

Analyte	Matrix	Dosing Day	Scheduled Time (hours)
TAK-071	Urine	1 and 42	Predose urine void within approximately 1 hour of dosing and (0 to 6), (6 to 12), and (12 to 24) hours postdose
TAK-071	Urine	21 and 62	(0 to 6), (6 to 12), and (12 to 24) hours postdose

Note: Subjects should void urine prior to dosing on Day 21 and 61.

Urine samples will not be collected from Cohorts 10 to 12, 17, 20 to 22.

The timing of the urine collection intervals may be adjusted based on the preliminary emerging PK data collected from prior cohort(s).

The amount of TAK-071 in urine will be summarized by TAK-071 dose level over each scheduled collection interval using descriptive statistics (N, arithmetic mean, SD, median, minimum, and maximum), separately for the TAK-071 SRD part ([Cohort 1 to 6, 18, and 19] for non-Japanese subjects), the MRD part (TAK-071 alone for non-Japanese subjects [Cohorts 7 to 9] and for Japanese subjects [Cohorts 13 to 15]), and subjects with MCI or Mild AD (Cohort 16). Individual urine concentration and amount data versus time interval along with urine volume will be presented in a data listing.

7.10.4 Urine Pharmacokinetic Parameters

The urine PK parameters of TAK-071 will be determined from the concentration-time profiles for all evaluable subjects by Takeda or its designee. Scheduled sampling times will be used in all computations involving urine collection times.

The following urine PK parameters of TAK-071 will be estimated:

Symbol/Term	Definition
Ae_t	Amount of drug excreted in urine from time 0 to time t for each interval and cumulative
$f_{e,t}$	Fraction of administered dose of drug excreted in urine from time 0 to time t for each interval and cumulative
CL_R	Renal clearance, calculated as Ae_t/AUC_t for Day 1 and Ae_t/AUC_{24} at steady-state

Additional urine PK parameters may be derived and/or reported as appropriate, in accordance with the CPAP.

Descriptive statistics (including N, arithmetic mean, SD, CV%, median, minimum and maximum) will be used to summarize the urine PK parameters for TAK-071 by TAK-071 dose level, separately for the TAK-071 SRD part ([Cohort 1 to 6, 18, and 19]) for non-Japanese subjects, the MRD part (TAK-071 alone for non-Japanese subjects [Cohorts 7 to 9] and for Japanese subjects [Cohorts 13 to 15]), and subjects with MCI or Mild AD (Cohort 16). Individual urine PK parameters will be presented in a data listing. Plots of individual and mean cumulative amounts excreted in urine vs time profiles will be produced.

7.10.5 CSF Pharmacokinetic Concentrations

Collection of CSF Samples for Pharmacokinetic Analysis Cohorts 3 and 9.

Analyte	Matrix	Dosing Day	Scheduled Time (hours)
TAK-071	CSF	1	Cohort 3: Predose (within 30 minutes before dosing) and at 0.5, 2, 4, 6, and 12 hours postdose
		28	Cohort 9: Predose (within 30 minutes before dosing) and at 4, 8, 12, 24 and 36 hours post last dose

If measured concentrations in Cohort 3 are excessively low, ie, most time points are below the limit of quantification of the assay, TAK-071 CSF concentrations may also be determined in subsequent SRD cohorts until a dose deemed to provide adequate brain penetration is identified (eg, a dose that provides CSF concentrations analogous to the efficacious free [estimated] plasma concentrations observed in preclinical animal models). A different criterion might be applied.

CSF sampling time points may be adjusted based on the preliminary emerging PK data; the total number of CSF samples collected per subject will not exceed the planned number.

The concentration of TAK-071 in CSF will be summarized by TAK-071 dose level over each scheduled sampling time using descriptive statistics (including N, arithmetic mean, SD, %CV, median, minimum, maximum, geometric mean and %CV of the geometric mean). Individual plasma concentration data versus time will be presented in a data listing. Additionally, graphical plots of individual and mean CSF concentration vs time profiles by treatment will be presented.

7.10.6 CSF Pharmacokinetic Parameters

The CSF PK parameters of TAK-071 will be determined from the CSF concentration-time profiles for all evaluable subjects according to standard noncompartmental analysis methods by Takeda or its designee. Actual sampling times, rather than scheduled sampling times, will be used in all computations involving sampling times. The following PK parameters will be calculated: CSF C_{max} following a single dose (Day 1) and at steady-state (after final dose following multiple dosing), CSF AUC_{12} following a single dose (Day 1) (Cohort 3 only) and CSF AUC_{36} at steady-state (after final dose following multiple dosing) (Cohort 9 only), and the ratio of CSF AUC_{12} to the plasma AUC_{12} (CSF AUC_{12} :plasma AUC_{12}) following a single dose (Cohort 3) and ratio of CSF AUC_{36} to the plasma AUC_{36} (CSF AUC_{36} :plasma AUC_{36}) at steady-state (Cohort 9). In the event that CSF sampling time points are adjusted in Cohort 9 following review of PK data from previous cohorts, ie, continuous sampling is extended to

48 hours postdose and then the corresponding AUC for the investigated time interval (ie, AUC₄₈) will be used instead of AUC₃₆. Additional CSF PK parameters may be derived and/or reported as appropriate.

Additional CSF PK parameters may be derived and/or reported as appropriate, in accordance with the CPAP.

CSF PK parameters for TAK-071 will be listed and summarized using descriptive statistics (including N, arithmetic mean, SD, %CV, median, minimum, maximum, geometric mean and %CV of the geometric mean). Geometric mean and geometric %CV will be presented for AUC and C_{max} only.

7.10.7 Pharmacodynamic Measurements

CCI

7.11 Other Outcomes

Not applicable.

7.12 Safety Analysis

Within each part (SRD cohorts, MRD cohorts, Cohort 16, and Cohort 17), for the non-Japanese and Japanese SRD and MRD cohorts separately, all safety summary tables will be presented by the pooled placebo group, each TAK-071 dose level, TAK-071 overall, and overall total within each part (SRD cohorts, non-Japanese MRD cohorts, Japanese MRD cohorts, Cohort 16, and Cohort 17) in the Safety Set. Safety data collected after administration of study drug under fed conditions will be summarized separately from data collected during administration of the same dose level under fasted conditions.

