7.12.1 Adverse Events

A PTE will be defined as any untoward medical occurrence in a clinical investigation subject who has signed informed consent to participate in a study but prior to study drug (TAK-071 or placebo) administration or increase in dose/start of donepezil prior to TAK-071 dose. A TEAE will be defined as an AE or a serious AE (SAE) that occurs or gets worse after receiving the first dose of study drug and within 30 days (onset date – last date of dose + 1 ≤ 30) after the last dose of study drug. A TEAE may also be a pretreatment AE or a concurrent medical condition diagnosed prior to the date of first dose of study drug that increases in severity after the start of dosing. AE data with onset occurring more than 30 days after last dose of study drug (AE start date – last dose date > 30) will be listed, but not included in the summary tables.

AE verbatim reported terms will be coded by system organ class, high-level term and preferred term using MedDRA, version to be delineated in the CSR.

TEAE summary tables will include numbers and percentages of subjects experiencing at least one AE by system organ class (SOC) and preferred term (PT) and will be tabulated for SRD

cohorts, non-Japanese MRD cohorts, Japanese MRD cohorts, Cohort 16, and Cohort 17. TEAEs will be summarized according to the treatment most recently received prior to the onset of the event. The TEAE summaries for SRD cohorts, non-Japanese MRD cohorts, Japanese MRD cohorts will also include a treatment group for TAK-071 overall, including all TEAEs summarized for any dose level of TAK-071.

The following is a list of AE summary tables to be generated:

- Overview of TEAEs.
- TEAEs by SOC and PT at subject and event level.
- Subject Mappings for TEAEs.
- TEAEs by PT.
- Most Frequent TEAEs by PT.
- Most Frequent Non-Serious TEAEs by PT.
- Relationship of TEAEs to Study Drug by SOC and PT.
- Drug-Related TEAEs by SOC and PT.
- Intensity of TEAEs by SOC and PT.
- Intensity of Drug-Related TEAEs by SOC and PT.
- Pretreatment Events by SOC and PT.

A subject with 2 or more different AEs within the same level of the MedDRA term and TAK-071 dose level and pooled placebo will be counted only once in that level using the most extreme incident for the intensity tables, and related events to study drug for the causality tables.

Most frequent TEAEs are defined as the AEs occurring in at least 2 subjects in any treatment (ie, pooled placebo or individual dose level).

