For MRD Japanese healthy volunteer Cohorts 13 to 15, blood samples for clinical laboratory tests (hematology, coagulation, serum chemistry, urinalysis) will be collected at Screening, at Check-in (Day -1), on Days 1, 2, 3, 8, 9, 10, 15, 20, 27, 28, 29, 30 (Final Visit)/ ET and at the Follow-up Visit. On Day 1, the urine sample for urinalysis will be taken predose (within 2 hours prior to dosing) and the blood sample for these tests will be taken 1 hour postdose. On subsequent days, samples will be taken predose upon rising in the morning under fasted condition.

For Cohort 16 in subjects with MCI or Mild AD, blood samples for clinical laboratory tests (hematology, coagulation, serum chemistry, urinalysis) will be collected at Screening, at Run-in Period (Day -21), at Check-in (Day -1), on Days 1, 2, 11, 20, 21, 22, 41, 42, 43, 52, 61, 62, 63 (Final Visit)/ ET and at the Follow-up Visit. On Days 1 and 41, the urine sample for urinalysis will be taken predose (within 2 hours prior to dosing) and the blood sample for these tests will be taken 1 hour postdose. On all other days, samples will be taken predose upon rising in the morning under fasted condition.

For BA/FE Cohort 17, blood samples for clinical laboratory tests (hematology, coagulation, serum chemistry, urinalysis) will be collected at Screening and in each period at Check-in (Day -1), 30 minutes postdose on Day 1, upon rising on Days 2 and 5 and, at PK visit on Day 8 (Day 8 of Period 3 is the final visit), at ET, if occurs, and Follow-up Visit (Day 12 [±2]) of Period 3, as appropriate.

Descriptive statistics (N, mean, median, SD, minimum and maximum) of clinical safety laboratory variables will be summarized by the pooled placebo group, each TAK-071 dose level, TAK-071 overall, and overall total within each part (SRD cohorts, MRD cohorts, Cohort 16, and Cohort 17) for baseline, each postdose time point, and change from period baseline to postdose

time points in International System of Units (SI). Only the scheduled measurements will be included in the summary. No statistical tests will be performed.

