and at 2, 4, 6, 8, and 12 hours postdose in the first 24 hours after the initial dose of TAK-071 and then daily afterwards while subjects are confined in the phase 1 unit.

For MRD Japanese healthy volunteer Cohorts 13 to 15, vital signs (oral temperature, respiration, pulse, and blood pressure) will be obtained at Screening, at Check-in (Day -1), on Days 1 through 30 (Final Visit)/ ET and at the Follow-up Visit. In addition, orthostatic blood pressure will be measured at predose and at 2, 4, 6, 8, and 12 hours postdose in the first 24 hours after the initial dose of TAK-071 and then daily afterwards while subjects are confined in the phase 1 unit.

For Cohort 16 in subjects with MCI or Mild AD, vital signs (oral temperature, respiration, pulse, and blood pressure) will be obtained at Screening, at Run-in Period (Day -49 and Day -21), at Check-in (Day -1), on Days 1, 2, 11, 20, 21, 22, 41, 42, 43, 52, 61, 62, and 63 (Final Visit)/ ET and at the Follow-up Visit. In addition, orthostatic blood pressure will be measured at predose and at 2, 4, 6, 8, and 12 hours postdose in the first 24 hours after the initial dose of TAK-071 and then afterwards on Days 2, 11, 20 to 22, 40 to 42, 51, and 60 to 62 (upon morning rising)/ ET.

For BA/FE Cohort 17, vital signs (oral temperature, respiration, pulse, and blood pressure) will be obtained at Screening and in each period at Check-in (Day -1), Day 1 (predose [within 45 minutes prior to dosing], and at 1, 3, and 12 hours postdose), and Days 2 through 5 (upon rising), Day 8 PK visit, Study Exit ([Day 8 of Period 3]/ ET and Follow-up Visit (Day 12 [±2]) of Period 3, as appropriate.

Descriptive statistics (N, mean, median, SD, minimum and maximum) of these vital signs will be summarized by the pooled placebo group, each TAK-071 dose level, TAK-071 overall, and overall total within each part (SRD cohorts, MRD cohorts, Cohort 16, and Cohort 17) for baseline, each postdose time point, and change from period baseline to postdose time points. Only the vital signs collected at the scheduled visits or time points will be included in the summary. No statistical tests will be performed for the observed vital signs.

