For MRD Japanese healthy volunteer Cohorts 13 to 15, a standard 12-lead ECG will be recorded at Screening, Check-in (Day -1), Days 1 and 8 (TAK-071 predose [within 60 minutes prior to dosing] and at 0.5, 1, 2, 4, and 8 hours postdose). On the remaining days during confinement 12-lead ECG be recorded (upon morning rising)/ ET and at the Follow-up Visit. Single ECGs will be taken at all visits.

For Cohort 16 in subjects with MCI or Mild AD, a standard 12-lead ECG will be recorded at Screening, Check-in (Day -1), Days 1, 21, 41, and 61 (TAK-071 predose [within 60 minutes prior to dosing] and at 0.5, 1, 2, 4, and 8 hours postdose), Days 2, 11, 20 to 22, 40 to 42, 51, and 60 to 62 (upon morning rising)/ ET and at the Follow-up Visit. Single ECGs will be taken at all visits.

For BA/FE Cohort 17, a standard 12-lead ECG will be recorded at Screening, and in each period at Check-in (Day -1), Day 1 (predose [within 45 minutes prior to dosing], and at 0.5, 1, 2, 4, and 8 hours postdose), Days 2 through 5 (upon morning rising), and Day 8 of Period 1 and 2, Study Exit (Day 8 of Period 3)/ ET, and Follow-up Visit Day 12 (± 2), as appropriate.

The investigator (or a qualified observer at the investigational site) will interpret the ECG using 1 of the following categories: within normal limits, abnormal but NCS, or abnormal and CS. The following parameters will be recorded from the subject's ECG trace: heart rate, RR interval, PR interval, QRS interval, and QTcF (QT interval with Fridericia correction method) and QTcB (QT interval with Bazett correction method) interval.

Descriptive statistics (N, mean, SD, median, minimum, and maximum) of the quantitative ECG results will be presented. The changes of ECG results from baseline results will be summarized by the pooled placebo group, each TAK-071 dose level, TAK-071 overall, and overall total within each part (SRD cohorts, MRD cohorts, Cohort 16, and Cohort 17).

All individual ECGs that meet Takeda's predefined criteria for MAV ([Appendix C](#)) will be listed. The number and percentage of subjects with at least one postdose markedly abnormal ECG measurement will be summarized. Subjects who meet the MAV criteria for postdose ECG will be mapped to their respective qualifying ECG result. All postdose MAV ECGs, including both scheduled and unscheduled measurements, will be included in the MAV summaries.

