Descriptive statistics by visit will be presented for the percentage of subjects with BSF scale scores ≥ 6 vs < 6 postbaseline compared with BSF scale scores ≥ 6 vs < 6 at Baseline and for the percentage of subjects with a change from Baseline in BSF scale score of ≥ 2 . Mean change from Baseline in BSF score and stool frequency will also be presented. Summary statistics (N, mean, SD, median, minimum, and maximum) will be generated for continuous variables (eg, time to first stool after dosing and stool frequency), and the number and percentage of subjects within each category will be presented for categorical variables (eg, stool consistency).

The results will be summarized by the pooled placebo group, each TAK-071 dose level, TAK-071 overall, and overall total within each part (SRD cohorts, MRD cohorts, and Cohort 16).

A plot of mean (\pm SD) bowel movement by study day by treatment will be presented.

All BSF data will be presented in a data listing.

7.12.5.3 *Columbia - Suicide Severity Rating Scale (C-SSRS)*

The C-SSRS is an instrument designed to systematically assess and track suicidal behavior and suicidal ideation throughout the trial. The C-SSRS has 4 domains, Suicidal Ideation, Ideation Intensity, Suicidal Behavior and Actual Suicide Attempts.

For SRD Cohorts 1 to 6 and 18 to 22, the C-SSRS will be performed at Screening, at Check-in (Day -1), Day 5 (Final Visit)/ ET. If clinically significant at Final Visit, C-SSRS will also be determined as part of the Follow-up Visit.

For MRD healthy volunteer Cohorts 7 and 8, the C-SSRS will be performed at Screening, at Check-in (Day -1), Day 23 (Final Visit)/ ET. If clinically significant at Final Visit, C-SSRS will also be determined as part of the Follow-up Visit.

For MRD healthy volunteer Cohort 9, the C-SSRS will be performed at Screening, at Check-in (Day -1), Day 30 (Final Visit)/ ET. If clinically significant at Final Visit, C-SSRS will also be determined as part of the Follow-up Visit.

For MRD + Donepezil pretreatment healthy volunteer Cohorts 10 to 12, the C-SSRS will be performed at Screening, at Check-in (Day -22), Day -1, Day 23 (Final Visit)/ ET. If clinically significant at Final Visit, C-SSRS will also be determined as part of the Follow-up Visit.

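### The SAP's safety tables have no donepezil factor, so the donepezil-alone versus TAK-071+donepezil safety comparison named in a primary objective is not tabulated

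*SAP*

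**What the plan says.** SAP 7.12 sets one column rule: "all safety summary tables will be presented by the pooled placebo group, each TAK-071 dose level, TAK-071 overall, and overall total within each part". The parts it names are SRD, non-Japanese MRD, Japanese MRD, Cohort 16 and Cohort 17. The detailed sections repeat the rule:

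- Laboratory (SAP 7.12.2): "laboratory variables will be summarized by the pooled placebo group, each TAK-071 dose level".
- Vital signs (SAP 7.12.3): "these vital signs will be summarized by the pooled placebo group, each TAK-071 dose level".
- ECG (SAP 7.12.4): "The changes of ECG results from baseline results will be summarized by the pooled placebo group, each TAK-071 dose level".
- Bowel function (SAP 7.12.5.2): "The results will be summarized by the pooled placebo group, each TAK-071 dose level, TAK-071 overall, and overall total within each part".

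SAP 7.12.1 defines frequent events by counts "in any treatment (ie, pooled placebo or individual dose level", so treatment there means placebo or a TAK-071 dose. Its attribution rule is: "TEAEs will be summarized according to the treatment most recently received prior to the onset of the event". The only further split in SAP 7.12 is fed versus fasted.

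SAP 7.1.3 places Cohorts 20 to 22 in SRD and Cohorts 10 to 12 in non-Japanese MRD. The donepezil cohorts therefore have no part of their own in the safety tables. The PK summaries (SAP 7.10.1 and 7.10.2) do report them separately.

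The objectives in SAP 4.1 ask for more. The second primary objective concerns TAK-071 safety in healthy subjects at steady-state donepezil. The fourth concerns the safety of a single 10 mg donepezil dose and its comparison with the combination. SAP 4.4.1 also commits to evaluating donepezil alone during the Cohort 10 to 12 pretreatment.

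**The concern.** The primary safety endpoints (SAP 5.1) are percentages of subjects, the cohort sizes have no power basis (SAP 6.0), and SAP 7.12.2 and 7.12.3 rule out tests on laboratory and vital-sign data. The column layout is in effect the primary safety analysis. If donepezil is not in the layout, two primary objectives lose the display that would answer them.

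The question is practical. Protocol 4.3 expects diarrhea, nausea and vomiting from TAK-071's pharmacology and anticipates possible synergy with donepezil. Protocol 6.2.2.4 names the same three effects as more frequent at the higher donepezil strengths, which include the 10 mg used in Cohorts 20 to 22. Event terms alone will not separate the drugs. These cohorts are meant to find a well-tolerated combination dose, and under SAP 7.13.1 the unblinded interim results support phase 2 protocol development.

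**Working it through.** **1. Check of the counts (SAP Table 4.a).** 8×8 + 3×12 + 2×8 + 8 + 3×8 + 3×6 + 8 + 12 = 64 + 36 + 16 + 8 + 24 + 18 + 8 + 12 = 186. This reproduces the stated total.

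**2. SRD part (100 subjects).** Cohorts 1 to 6, 18 and 19 allocate 6 active and 2 placebo each. Cohorts 20 to 22 allocate 3 double placebo, 3 donepezil only and 6 combination each.

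- Placebo without donepezil: 8×2 + 3×3 = 25
- Donepezil only: 3×3 = 9
- TAK-071 alone: 8×6 = 48
- TAK-071+donepezil: 3×6 = 18

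Where the 9 donepezil-only subjects go depends on how the attribution rule is read:

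- If donepezil counts as a treatment, it has no column. Placebo and TAK-071 then hold 25 + 66 = 91 of 100 subjects, and the 9 appear only in the overall total.
- If it does not, their most recent treatment is TAK-071 placebo. Pooled placebo is then 34, of whom 9 (26%) took donepezil.

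Neither reading shows 9 against 18. In both, TAK-071 overall is 66, of whom 18 (27%) were assigned donepezil.

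**3. SRD timing.** Protocol 8.1.3 and note (b) to SAP Table 4.a put donepezil about 24 hours after TAK-071, on Day 2. The 1-hour laboratory sample, the 2 to 12 hour orthostatic readings and the 0.5 to 8 hour ECGs all fall on Day 1, before any donepezil. Mixing can therefore affect only data after the Day 2 dose, and tables that accumulate over the study (TEAEs and markedly abnormal values).

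**4. Non-Japanese MRD part (48 subjects).** Placebo is 3×2 without and 3×2 with donepezil (6 and 6); TAK-071 is 3×6 and 3×6 (18 and 18). Protocol 6.2.2.2 intends Cohorts 10 to 12 to repeat the doses of Cohorts 7 to 9. Each dose column is then (6a + 6b)/12, with a and b the rates without and with donepezil. Placebo has the same half-and-half mix, so a pure donepezil effect cancels. An excess D of TAK-071 over placebo that occurs only with donepezil is shown as D/2: assumed values of 20, 30 and 40 points appear as 10, 15 and 20.

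**5. Lead-in.** All 3×8 = 24 subjects of Cohorts 10 to 12 take donepezil alone from Day -21 to Day -1. Protocol Appendix A records events from the first donepezil dose as AEs. They are not pretreatment events either, because SAP 7.12.1 ends that period at TAK-071 or placebo dosing "or increase in dose/start of donepezil prior to TAK-071 dose". No TEAE column matches them.

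**6. Illustration for cumulative SRD tables (assumed rates, no TAK-071 effect).** Let p0 and p1 be event rates without and with donepezil, and s the donepezil share of a dose column. Then s = 6/6 = 1 if no TAK-071-alone cohort had that dose, and s = 6/12 = 0.5 if one did. The excess over placebo is s(p1 − p0) with n=25, or (s − 9/34)(p1 − p0) with n=34.

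| Assumed p0/p1 | s=1, n=25 | s=1, n=34 | s=0.5, n=25 | s=0.5, n=34 |
|---|---|---|---|---|
| 5/15% | 10 points | 7.4 | 5 | 2.4 |
| 10/30% | 20 | 14.7 | 10 | 4.7 |
| 20/50% | 30 | 22.1 | 15 | 7.1 |

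For TAK-071 overall at 10/30%: 18/66 × 20 = 5.5 points (n=25), or (18/66 − 9/34) × 20 = 0.2 (n=34). For scale, one event in a column of 6 is 16.7 points.

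**The case against.** **Timing.** Because donepezil comes a day after TAK-071, Day 1 results cannot carry a donepezil effect. This stands. A reader might infer that every combination column in SRD is distorted by donepezil. The documents do not support that: a 6-of-6 share describes arm assignment, and the intensive post-dose safety sampling precedes the donepezil dose.

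**Table 4.a.** It lists the donepezil cohorts as separate design groups, and unseen table shells might follow it. That is possible, but SAP 7.12 speaks of all safety summary tables, names the parts and columns itself, and provides none for donepezil. A design overview does not override it.

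**Attribution.** It would be too strong to say that the 9 donepezil-only subjects certainly have no column. SAP 7.1 pools data from periods on placebo, which supports counting them there. Only the absence of the comparison is common to both readings.

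**Recoverability.** Individual data are listed, and the SAP plans subject mappings for TEAEs and for markedly abnormal laboratory, vital-sign and ECG values. With 3 to 6 subjects per arm per cohort, regrouping is easy. Some lead-in visit days also do not exist for Cohorts 7 to 9, so any by-visit rows for them would hold only Cohort 10 to 12 subjects. This lowers the urgency, but a regrouping after unblinding is not the planned comparison.

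**Doses.** The 40 mg overlap rests on an SRD escalation given for illustration in Protocol 6.2.2.2, and actual doses may differ.

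**Conclusion.** The point holds for the summary tables. As written, the SAP does not tabulate the 9 versus 18 safety comparison of the fourth primary objective. It shows the second objective only as an average of subjects with and without donepezil if doses match as intended. It gives the 24-subject lead-in no column.

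The main defect is the missing comparison, not a measured bias. The percentage-point figures rest on assumed event rates, and most are of the order of one event in a small column. A reader might infer that the non-Japanese MRD tables would show a false TAK-071 effect; with matched doses the spurious difference is zero, and the cost is dilution by half. A reader might also infer that the data are lost; they are not.

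Because the trial is descriptive and listings and mappings permit a rebuild, this should be fixed before the tables are produced but does not threaten the study.

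**What to change.** Define the columns of the tabulated safety summaries (SAP 7.12, 7.12.1 to 7.12.4 and 7.12.5.2) by part and donepezil status:

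- **SRD:** placebo without donepezil (25); donepezil alone (9); TAK-071 alone by dose; TAK-071+donepezil by dose and overall (18).
- **Non-Japanese MRD:** placebo (6); donepezil+placebo (6); TAK-071 alone by dose; TAK-071+donepezil by dose.
- **Cohort 10 to 12 lead-in:** donepezil alone, in its own table (24).

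State how the most-recent-treatment rule applies to the lead-in and to Cohorts 20 to 22. In the latter, show events before the Day 2 donepezil or placebo dose separately from those after it. Otherwise the new columns would put Day 1 events under a donepezil label. Align the placebo-pooling sentences: Protocol 13.1.5 pools across cohorts within SRD and MRD, while SAP 7.1 refers to each cohort. Items that are only listed (physical examination, C-SSRS, MMSE, lumbar x-ray) need no change.

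The cost is SAP wording and table shells, with no new data. The downside is smaller descriptive comparators: 25 and 9 in SRD, and 6 and 6 instead of 12 in non-Japanese MRD.
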